6.1.2 Secondary Objectives

- To determine the tolerability of a single dose [REDACTED] of LT3001 drug product administered IV in subjects with AIS.
- To determine the potential efficacy of a single dose [REDACTED] of LT3001 drug product administered IV in subjects with AIS.

6.2 Study Endpoints

6.2.1 Primary Endpoint

The primary endpoint of this study is the occurrence of symptomatic intracranial hemorrhage (sICH) within 36 hours after dosing -- clinical deterioration defined as an increase in the National Institute of Health Stroke Scale (NIHSS) of 4 points or more AND confirmed by computed tomography (CT)- or magnetic resonance imaging (MRI)- documented.

6.2.2 Secondary Endpoints

6.2.2.1 Safety and Efficacy Endpoints

The secondary efficacy and safety endpoints are as follows:

- The occurrence of sICH [REDACTED].
- The occurrence of asymptomatic intracranial hemorrhage (ICH) [REDACTED].
- The occurrence of mortality due to intracerebral or other major bleeding complications [REDACTED].
- The occurrence of mortality due to any reason [REDACTED].
- The number and severity of AEs [REDACTED].
- The number of subjects with AEs [REDACTED].

- The occurrence of recurrent stroke [REDACTED].
- Functional outcome
 - The frequency and percentage of subjects with each grade on modified Rankin Scale (mRS) [REDACTED].
 - The frequency and percentage of subjects [REDACTED].
- Neurological outcome
 - Absolute change in NIHSS [REDACTED].
 - The proportion of subjects with NIHSS ≤ 2 [REDACTED].

[REDACTED]

[REDACTED]

[REDACTED]

[REDACTED]

[REDACTED]

7 INVESTIGATIONAL PLAN

7.1 Description of Overall Study Design and Plan

This is a multicenter, double-blind, single-dose, randomized, and placebo-controlled prospective Phase IIa clinical study, designed to evaluate LT3001 drug product versus placebo/control in subjects with AIS.

There is only one dose of LT3001 drug product [REDACTED]. The dose is based on the results from nonclinical studies, the FIH study in healthy human volunteers (LT3001-101), and US FDA recommendations. Approximately 24 eligible subjects will be randomized 2:1 to LT3001 drug product or placebo. Each eligible subject will receive a single dose of LT3001 drug product or placebo within 24 hours after stroke symptoms onset. LT3001 drug product or placebo will be administered via a [REDACTED] IV infusion. The infusion will be stopped if an SAE occurs during infusion.

The participation for each subject is approximately 92 days from the screening visit (Visit 1) to the last visit. The study design is illustrated in [Figure 1](#). The Schedule of Assessments is provided in [Section 10](#).

7.2 Discussion of Study Design

For this first study in subjects with AIS, a single-dose placebo-controlled design is chosen.

Because there is no approved drug treatment for AIS for administration beyond 3 hours of stroke onset in the US and beyond 3 to 4.5 hours of stroke onset in Taiwan, a placebo-controlled study

will be ethically acceptable in order to evaluate the drug effect objectively. Preliminary efficacy will be evaluated by assessing the infarct volume, occurrence of recurrent stroke, functional outcome measured by mRS, and neurological outcome measured by the NIHSS.

The dose and regimen chosen is based on results from the nonclinical studies, FIH healthy volunteer study, and US FDA recommendations.

7.3 End of Study

A subject will have fulfilled the requirements for study completion when the subject has completed all study periods, including the last scheduled follow-up visit as indicated in the Schedule of Assessments ([Table 10-1](#)).

The end of the study will be the last subject's last visit.

8 SELECTION OF STUDY POPULATION

Section 7.1 provides information regarding number of subjects planned to be randomized.

8.1 Inclusion Criteria

Individuals must meet all of the following criteria to be included in the study:

1. Subject or subject's legal representative consented to participation by signing the informed consent form (ICF) after receiving full information about the study.
2. Subject is aged 18 to 90 years, inclusive, at the time of Screening [REDACTED].
3. Subject has a NIHSS of 4 to 30.
4. Subject has a clinical diagnosis of AIS within 24 hours after stroke symptoms onset.
5. [REDACTED]
6. Subject is able to receive the investigational product within 24 hours after stroke symptoms onset.
7. Subjects are women of childbearing potential (WOCBP) or men whose sexual partners are WOCBP, are able and willing to use at least 1 highly effective method of contraception during the study until 3 months after dosing of investigational product.

8.2 Exclusion Criteria

Individuals meeting any of the following criteria at Screening [REDACTED] or Baseline are ineligible to participate in this study:

1. Subject has been treated with rtPA and/or endovascular thrombectomy (EVT) during the current AIS.
2. Subject has a pre-stroke disability that requires help for activities of daily living [REDACTED].
3. Subject has imaging evidence of acute intracranial hemorrhage, intraparenchymal tumor, arteriovenous malformations, other central nervous system lesions that could increase the risk of bleeding, or aneurysm requiring treatment.
4. [REDACTED]
5. Subject has symptoms of suspected subarachnoid hemorrhage, [REDACTED].
6. Subject has generalized seizure [REDACTED].
7. Subject has current uncontrolled hypertension [REDACTED].
8. Subject has International Normalized Ratio (INR) >1.7, abnormal activated partial thromboplastin time (aPTT) or platelet count <100,000/mm³.
9. Subject has blood glucose concentration <50 mg/dL or >400 mg/dL.
10. Subject is lactating, pregnant (pregnancy test required for all female subjects), or planning to become pregnant during the study.
11. Subject has received anticoagulants within 48 hours prior to treatment, e.g., direct oral anticoagulants (e.g., dabigatran, rivaroxaban, apixaban, edoxaban), low molecular weight heparin (e.g., enoxaparin), fondaparinux.
12. Subject has received oral dual antiplatelet therapy and glycoprotein (GP) IIb/IIIa inhibitors within 48 hours prior to treatment.
13. Subject has had prior AIS, myocardial infarction, or serious head trauma within 90 days of Screening [REDACTED].
14. Subject has history of ICH within 90 days of Screening [REDACTED].
15. Subject has had any major surgery within 90 days of Screening [REDACTED], e.g., intracranial or intraspinal surgery, coronary artery bypass graft, obstetrical delivery, organ biopsy.
16. Subject with bleeding event within 21 days of Screening [REDACTED], e.g., gastrointestinal or hemorrhage.

17. Subject has puncture of noncompressible vessels within 7 days of Screening [REDACTED].
18. Subject has severe hepatic, renal, and/or active infectious disease at Screening [REDACTED].
19. Subject has participated in another investigational study and received investigational product within 30 days of Screening [REDACTED] or 5 half-lives (whichever is longer).
20. In the opinion of the Investigator, the subject is not appropriate for the study for any other reason.

8.3 Rescreening

Individuals who sign the ICF to participate in the study but who do not subsequently meet all the requirements as outlined in the inclusion and exclusion criteria and therefore do not enroll (screen failures) may be rescreened if they have another episode of stroke ≥ 90 days after the previous one.

8.4 Study Withdrawal, Removal, and Replacement of Subjects

If a subject discontinues study treatment and is withdrawn from the study for any reason, the study site must immediately notify the Medical Monitor (see contact details in [Section 12.7.3](#)). The date and the reason for study discontinuation must be recorded on the electronic case report form (eCRF). Subjects who discontinue early from the study will be asked to return to the study site within to complete Early Termination assessments as indicated in the Schedule of Assessments ([Table 10-1](#)).

In the event that a subject discontinues prematurely from the study because of a treatment-emergent AE (TEAE) or serious TEAE, the TEAE or serious TEAE will be followed up until it resolves (returns to normal or baseline values) or stabilizes, or until it is judged by the Investigator to no longer be clinically significant.

Once a subject is withdrawn from the study, the subject may not re-enter the study.

A subject may voluntarily withdraw or be withdrawn from the study at any time for reasons including, but not limited to, the following:

- unacceptable toxicity or AE.
- subject withdrawal of consent: at any time, a subject's participation in the study may be terminated at his/her request or on the basis of the Investigator's clinical judgment. The reason for subject withdrawal will be noted on the eCRF.
- intercurrent illness: a condition, injury, or disease unrelated to the primary diagnosis that became apparent during treatment and necessitated the subject's termination from the study.
- general or specific changes in the subject's condition that renders him/her ineligible for further treatment according to the inclusion/exclusion criteria.

- subject fails to adhere to the protocol requirements (e.g., drug noncompliance, failure to return for defined number of visits).
- lost to follow-up: the subject stopped coming for visits, and study personnel were unable to contact the subject 3 times.
- pregnancy, as indicated in [Section 12.7.5](#).

Additionally, the Sponsor may stop the study at any time for safety, regulatory, legal, or other reasons aligned with Good Clinical Practice (GCP). This study may be terminated at the discretion of the Sponsor or any regulatory agency. An Investigator may elect to discontinue or stop the study at his or her study site for any reason, including safety or low enrollment.

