	
h) International Normalized Ratio (INR) >1.7 and/or abnormal activated partial thromboplastin time (aPTT) or platelet count <100,000/mm³; i) blood glucose concentration <50 mg/dL or >400 mg/dL; j) lactating or pregnant subjects or those planning to become pregnant during the study (pregnancy test required for all female subjects); k) received anticoagulants and/or oral dual antiplatelet therapy and glycoprotein IIb/IIIa inhibitors within 48 hours prior to treatment; l) any of the following within 90 days of Screening (Visit 1) - prior AIS, myocardial infarction, serious head trauma, history of ICH, or major surgery; m) bleeding event within 21 days of Screening (Visit 1); n) puncture of noncompressible vessels within 7 days of Screening (Visit 1); and o) severe hepatic, renal, and/or infectious disease at Screening (Visit 1).

Planned Sample Size:	Approximately 24 eligible subjects will be randomized 2:1 to LT3001 drug product or placebo.
Investigational Therapy:	LT3001 drug product [REDACTED]
Reference Therapy:	Placebo [REDACTED]
Treatment Duration:	All subjects will receive a single dose of investigational product on Day 0. The participation for each subject is approximately 92 days from the screening visit [REDACTED] to the last visit. The whole study is expected to last for approximately 12 months (first subject first visit [FSFV] to last subject last visit [LSLV]).
Safety:	
The primary safety endpoint is the occurrence of sICH within 36 hours after dosing and will be assessed via NIHSS and imaging (CT or MRI). [REDACTED]
 
[REDACTED] Additional evaluations include the occurrence of asymptomatic ICH, mortality due to intracerebral or other major bleeding complications, mortality due to any reason, and the incidence of AEs, including the relationship to study treatment and severity.

Efficacy:	
Functional outcome will be assessed using the mRS and neurological outcome will be assessed using the NIHSS [REDACTED]
 
[REDACTED] The occurrence of recurrent stroke [REDACTED]

	[REDACTED]

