### **6.3. Missing Data**

Missing data will not be estimated and/or imputed in any way. Adverse events(AEs) with missing onset dates will be included as treatment-emergent.

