## 7. Demographic, Other Baseline Characteristics and Medication

### 7.1. Subject Disposition and Withdrawals

Subject disposition will be summarized and listed.

The number and percentage of subjects in each population, completed and discontinued the study, together with the reasons for discontinuation (unacceptable toxicity or AE, subject withdrawal of consent, intercurrent illness, general or specific changes in the subject's condition, subject fails to adhere to the protocol requirements, lost to follow-up, pregnancy, study terminated, other) will be presented.

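### With one Day 0 dose, the adverse-event and ineligibility withdrawal reasons in Protocol 8.4 can, after dosing, only end follow-up, and can do so selectively in harmed subjects

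*Protocol*

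**What the plan says.** Protocol 8.4 opens its list of reasons with "A subject may voluntarily withdraw or be withdrawn from the study at any time". The list includes unacceptable toxicity or an adverse event, and a change in condition that "renders him/her ineligible for further treatment according to the inclusion/exclusion criteria". The consent bullet also allows termination on the investigator's clinical judgment. Withdrawal is final: "Once a subject is withdrawn from the study, the subject may not re-enter the study".

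The Protocol synopsis fixes the treatment: "All subjects will receive a single dose of investigational product on Day 0". Stopping the infusion has its own rule in Protocol 7.1: "The infusion will be stopped if an SAE occurs during infusion".

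Protocol 8.2, exclusion 3, reads in part "Subject has imaging evidence of acute intracranial hemorrhage". Imaging confirmation is also one half of the primary endpoint, sICH within 36 hours (Protocol 6.2.1). Protocol 12.1 records symptomatic and asymptomatic ICH to 36 hours and to 7 days.

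For analysis, SAP 6.3 states "Missing data will not be estimated and/or imputed in any way". SAP 10.10 and 10.11 use only assessable subjects as the denominator for sICH and asymptomatic ICH. The per-protocol set requires completion through Day 90 (SAP 5.5). SAP 7.1 carries a shortened form of the withdrawal reason into disposition: "general or specific changes in the subject" and the word condition, without the ineligibility clause.

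**The concern.** The ineligibility reason suits a repeated-dose trial, where failing a criterion midway is grounds for giving no more drug. Here there is no second dose. Protocol 8.4 does not distinguish stopping treatment from leaving the study, so after the infusion the only thing these reasons can stop is observation.

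The subjects most open to withdrawal are those with an adverse event or a new bleed, so missingness can depend on the outcome under study. If the drug caused harm, the LT3001 arm could lose some of its worst later NIHSS and mRS results. An asymptomatic bleed that later became symptomatic might also go unassessed. With 24 subjects, one or two such losses are visible in every percentage.

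**Working it through.** **1. What the reasons can do, by time.**
- Before dosing: the ineligibility reason has a purpose, because treatment is still ahead.
- During the infusion: Protocol 7.1 has a separate stopping rule for an SAE.
- After the infusion: no treatment remains, so withdrawal for an adverse event or ineligibility ends only scheduled follow-up, irreversibly.

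**2. Link to outcome.** A bleed on post-dose imaging has the same content as exclusion 3. Protocol 9.5.1 refers to repeat brain imaging at 24 hours, so bleeds are looked for when the reason could be invoked. Read literally, the wording is not confined to bleeders: a subject whose NIHSS falls below 4 or rises above 30 no longer meets inclusion 3 (NIHSS 4 to 30).

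**3. What remains after withdrawal.** Early Termination assessments; follow-up of the treatment-emergent event if it caused the discontinuation (Protocol 8.4); SAE reporting to 3 months after treatment (Protocol 12.7.3). No visible text keeps the subject in scheduled NIHSS or mRS assessments. Data from unscheduled visits go to listings only (SAP 6.1).

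**4. Arm sizes.** The only planning figure is 24 subjects at 2:1: 24 × 2/3 = 16 and 24 × 1/3 = 8. One lost subject is 1/16 = 6.25% (6.3%) of LT3001 or 1/8 = 12.5% of placebo.

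**5. Chance that the situation arises.** The visible text gives no ICH rate, so a range is assumed. P(at least one bleed among 16) = 1 − (1 − q)^16:
- q = 2%: 27.6%
- q = 5%: 56.0%
- q = 10%: 81.5%
- q = 20%: 97.2%

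**6. Illustration for mRS 0-2 (assumed counts).** Let r of 16 LT3001 subjects reach 0-2, and let k subjects with poor outcomes be withdrawn. Full follow-up gives r/16; an observed-only denominator gives r/(16 − k).
- r = 8: 8/16 = 50.0% becomes 8/15 = 53.3%, 8/14 = 57.1% or 8/13 = 61.5% for k = 1, 2, 3.
- Smallest shift for r = 4, 8 or 12 and k = 1 to 3: 4/15 − 4/16 = 1.7 points. Largest: 12/13 − 12/16 = 17.3 points.

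The observed-only denominator is that of SAP 14.2.5.2. SAP 6.1 instead uses the whole population unless otherwise stated. Under that rule the rate stays r/16 and the shift is zero, although the k poor grades disappear from the by-grade mRS table.

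**7. Illustration for sICH (assumed).** One asymptomatic bleed is withdrawn before becoming symptomatic, and the subject is then not assessable. The result 1/16 = 6.3% (upper limit of the two-sided 95% exact interval 30.2%) becomes 0/15 = 0% (upper limit 21.8%).

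**The case against.** The strongest reply is that the trigger cannot fire after dosing. If no further treatment exists, nobody can become ineligible for it, and Protocol 8.2 applies its criteria at Screening or Baseline. That is a fair reading, but Protocol 8.4 invokes the same criteria with effect at any time, so a site could read it either way. The adverse-event reason needs no such reading.

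Several stronger inferences do not stand:
- A reader might infer that the plan directs sites to withdraw subjects who bleed. It does not; the wording is permissive.
- A reader might infer that bleeds would go uncounted. A documented bleed already counts for the ICH endpoints, and a confirmed sICH within 36 hours is already a primary event. Deaths should still arrive through SAE reporting.
- Seizure and uncontrolled hypertension (exclusions 6 and 7) might be taken as trial outcomes too. They are not among the visible endpoints, and their qualifiers are blacked out.
- The intercurrent-illness and drug-noncompliance reasons barely apply after a completed, supervised infusion: the first is limited to an unrelated condition appearing during treatment.

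Withdrawal reasons and events leading to discontinuation are also tabulated, so selective loss among 24 subjects would be noticeable. Noticing it does not recover the missing NIHSS and mRS values. Table 10-1 and the visit sections are not shown, so a retention rule there, or NIHSS and mRS at Early Termination, cannot be ruled out. A single Early Termination visit would still not replace a Day 90 outcome.

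**Conclusion.** The point holds as a gap in the withdrawal rule. After the single dose, Protocol 8.4 permits follow-up to end for reasons related to harm, when no treatment is left to stop. The exposure is later conversion to sICH (to 36 hours or 7 days) and scheduled NIHSS and mRS assessments through Day 90, with no imputation and removal from the per-protocol set.

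The firm size is 6.3% of the LT3001 arm or 12.5% of placebo per lost subject, assuming exactly 16 and 8. A reader might take the shift from 50.0% to 57.1% as the expected bias. The documents do not support that: it needs two withdrawn subjects with poor outcomes, both assumed, and the SAP 14.2.5.2 denominator. Under SAP 6.1 it is zero. The broader inference that LT3001 would look safer overall is also too strong; for safety, the exposure is chiefly later conversion of a bleed. The conclusion assumes that no retention rule sits in the text that is not shown.

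**What to change.** Reconcile Protocol 8.4 with the single-dose design by separating the stopping of investigational product from leaving the study. State that a subject who has received any investigational product, and then has an adverse event, a bleed or a change in eligibility status, stays in the scheduled safety, NIHSS and mRS assessments through Day 90. The exceptions would be withdrawn consent, loss to follow-up, death, or termination of the study or site.

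Three matching changes are needed:
- Apply the statement to the investigator's-judgment clause inside the consent bullet; otherwise the same route stays open.
- Reconcile it with the pregnancy provisions (Protocol 8.4 and 12.7.5) and the rule on discontinuing unblinded subjects (Protocol 9.3.2).
- Align the disposition reasons in SAP 7.1 so that stopping product and ending follow-up are recorded separately.

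The clinical grounds for stopping the infusion are untouched. The conflict between SAP 6.1 and 14.2.5.2 on denominators should be settled in the same revision. The core change costs one paragraph in a protocol amendment and a revised disposition list, with no new visits.

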9 TREATMENTS

9.1 Details of Study Treatments

Eligible subjects will be randomized 2:1 to LT3001 drug product [REDACTED] and placebo.

LT3001 drug product will be provided [REDACTED] in glass vials with butyl rubber stoppers and flip-off aluminum crimp seals. Each vial will contain LT3001 drug substance.

[REDACTED]

[REDACTED]

[REDACTED]

All drug supplies will be provided by the Sponsor.

9.2 Dosage Schedule

Subjects randomized to LT3001 drug product will receive a single dose of LT3001 drug product [REDACTED]. Subjects randomized to placebo will receive placebo [REDACTED] as well.

9.3 Measures to Minimize Bias: Study Treatment Assignment and Blinding

The study is placebo-controlled to lessen the risk that events due to chance are falsely attributed to LT3001 drug product.

The study is randomized to control for factors known and unknown between the treatment groups.

The study is blinded so that the subjects, site staff administering the study treatment (LT3001 drug product or placebo), and site staff conducting study assessments will not know which treatment a subject receives to allow assessment of the study objectives without bias.

9.3.1 Method of Study Treatment Assignment

Subjects will be randomly assigned to receive LT3001 drug product or placebo in a ratio of 2:1.

At Screening [REDACTED] will assign a unique subject identification number to the subject known as the Subject Number. This number

will be associated with the subject throughout the study. [REDACTED]

The subjects will be centrally randomized at a study level. The treatment assignment will be determined by a randomization list prepared by the biostatistics group [REDACTED]

9.3.2 Blinding

According to the randomization schedule as indicated in the Schedule of Assessments (Table 10-1) and in accordance with the pharmacy manual, the Investigator or designee will obtain the Randomization Number [REDACTED], and the Investigator or designee at the study site will be responsible to provide the Subject Number, Randomization Number [REDACTED] to the unblinded pharmacist or designee for the calculation of study treatment dosage. The unblinded pharmacist or designee will further confirm the Subject Number, Randomization Number, and the study treatment group. [REDACTED]

[REDACTED] Prepared study treatments will be identical in appearance and labeled in a blinded manner. Information included on the label includes the Protocol Number, Subject Number, Randomization Number, etc. No other study site personnel, subjects, Sponsor personnel, or Sponsor designees will be unblinded to treatment assignment throughout the duration of the study unless unblinding is required. If an Investigator becomes unblinded to a given subject's study treatment, that subject will be discontinued from the study unless there are ethical reasons for that subject not to be discontinued; approval from the Medical Monitor must be obtained in such instances.

The Investigator must make every effort to contact the Medical Monitor prior to unblinding a subject (contact provided in Section 12.7.3). In the rare event that contact with the Medical Monitor is not possible prior to unblinding, the Investigator reserves the right to unblind in a true emergency, where subject safety is at immediate risk. The unblinding and its cause will also be documented in the eCRF [REDACTED].

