14.2 Analysis Populations

Enrolled Population

The enrolled population will include all individuals who sign the ICF.

Intent-to-Treat (ITT) Population

The ITT population will include all subjects who are randomized, irrespective of any deviation from the protocol or premature discontinuation. The treatment group assignment will be designated according to initial randomization. The ITT population will serve as the primary basis for the analysis of efficacy.

Per-Protocol (PP) Population

The PP population will comprise all ITT subjects who complete study procedures through Day 90 without a major protocol deviation. The PP population will also be used for the analysis of efficacy.

Safety Population

The safety population will include all randomized subjects who receive at least 1 dose of investigational product. The treatment group assignment in this population will be defined by the treatment actually received. This population will be used for the analysis of safety.

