### **5.4.**

### **5.5. Per-Protocol (PP) Population**

The PP population will comprise all ITT subjects who complete study procedures through Day 90 without a major protocol deviation potentially impacting efficacy measurements. The PP population will also be used for the analysis of efficacy.

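### Investigator unblinding after the single dose ends a subject's scheduled follow-up by default, although no study treatment is left to stop

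*Protocol*

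**What the plan says.** Protocol 9.3.2 (Blinding) deals with the case where an Investigator learns a subject's treatment: "that subject will be discontinued from the study unless there are ethical reasons for that subject not to be discontinued". The exception also needs the Medical Monitor's approval. SAP 3.6 repeats the rule and adds nothing on how the data are then analysed. Contact with the Medical Monitor is expected before unblinding, but if that is not possible "the Investigator reserves the right to unblind in a true emergency, where subject safety is at immediate risk".

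The design around the rule is as follows.

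- Dosing (Protocol Synopsis, Treatment Duration): "All subjects will receive a single dose of investigational product on Day 0".
- Duration (Protocol 7.1): "The participation for each subject is approximately 92 days from the screening visit (Visit 1) to the last visit".
- Leaving the study (Protocol 8.4): "Once a subject is withdrawn from the study, the subject may not re-enter the study". Early Termination assessments are requested, and a treatment-emergent AE that led to discontinuation is followed until it resolves, stabilizes or is no longer clinically significant.
- ITT (Protocol 14.2; SAP 5.3): all randomized subjects, "irrespective of any deviation from the protocol or premature discontinuation". This is the primary set for efficacy.
- PP (SAP 5.5): "all ITT subjects who complete study procedures through Day 90 without a major protocol deviation potentially impacting efficacy measurements". Protocol 14.2 has the same definition without the last four words.
- Missing data (SAP 6.3): no imputation of any kind.

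**The concern.** The rule discontinues the subject from the study, not merely from treatment. No readable passage confines it to the period before or during the infusion, although parts of Protocol 9.3.2 are redacted. Once the single infusion is over, applying it withdraws no study treatment and costs the remaining scheduled visits.

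Those visits carry the later mRS and NIHSS assessments and observation for recurrent stroke to 90 days (Protocol 14.4.1). If the unblinding falls before Day 7, they may also carry the 7-day ICH assessment (Protocol 12.1). The ITT set keeps the subject as a member while the conduct rule stops collection of the outcomes that the ITT summaries use.

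The loss may be informative. Unblinding without first reaching the Medical Monitor is reserved for immediate risk to the subject, and safety is the primary objective. With planned arms of about 16 and 8, one such subject is a visible share of an arm.

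**Working it through.** The documents give no figure to reproduce here: no unblinding rate, dropout rate or assumed mRS response. The check compares the provisions and then illustrates the size.

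**1. What remains to stop, and what is cut.** After a completed infusion, 1 planned dose - 1 given = 0 doses left. If unblinding occurs on day d after dosing, the share of the 90-day period removed is (90 - d)/90:

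- 24 hours: 89/90 = 98.9%
- 36 hours: 88.5/90 = 98.3%
- Day 7: 83/90 = 92.2%

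**2. What continues.** Early Termination assessments and follow-up of the causative AE (Protocol 8.4) continue, as does SAE reporting for 3 months after treatment (Protocol 12.7.3). A known death scores mRS 6 (Protocol 14.4.4), so deaths are not counted as lost. The Schedule of Assessments is redacted. SAP 10.5 shows an Early Termination time point for vital signs, but whether mRS or NIHSS is taken then cannot be read.

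**3. Analysis sets.** Membership of ITT and Safety is unchanged. PP membership is lost whatever the Early Termination visit contains, because PP requires study procedures to be completed through Day 90.

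**4. Size.** 24 subjects at 2:1 give 24 × 2/3 = 16 and 24 × 1/3 = 8. One subject is 1/16 = 6.3% or 1/8 = 12.5% of the arm.

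Assumptions: exactly one surviving subject is unblinded after dosing, the exception is not used, no later mRS is obtained, and the true mRS 0-2 rates are 8/16 and 4/8. The SAP has two general denominator rules: the relevant population (6.1) and subjects with an observation (14.2.5.2). That is a separate matter, so the results are kept apart.

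| ITT denominator | Subject lost | LT3001 | Placebo |
|---|---|---|---|
| Observed cases | mRS 3-5 | 8/15 = 53.3% | 4/7 = 57.1% |
| Observed cases | mRS 0-2 | 7/15 = 46.7% | 3/7 = 42.9% |
| Population | mRS 3-5 | 8/16 = 50.0% | 4/8 = 50.0% |
| Population | mRS 0-2 | 7/16 = 43.8% | 3/8 = 37.5% |

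In PP the set itself shrinks to at most 15 or 7. If all the others qualify, the observed-case figures apply under either rule.

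For scale, the exact (Clopper-Pearson) 95% interval is 24.7% to 75.3% for 8/16 and 15.7% to 84.3% for 4/8.

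**5. How likely.** If each subject had an assumed 2%, 5% or 10% chance of being unblinded at any time, the chance of at least one among 24 is 1 - (1 - p)^24 = 38%, 71% or 92%. These rates are illustrative. The true rate may well be low.

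**The case against.** **The rule has a purpose.** Bleeding is classified by the Investigator or a designee (Protocol 12.1), and blinding is there to protect the assessments from bias (Protocol 9.3). Discontinuing the subject keeps ratings by an unblinded Investigator out of the data. This stands, and a reader who infers that the rule does nothing after dosing goes too far. Flagging those ratings gives the same protection, since they can be identified and set aside, and the subject is not lost.

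**A blinded rater may not exist.** Protocol 9.3 says that assessing staff are blinded. A reader might infer that they are different people from the Investigator, but the text does not say so. The fix must therefore work where the Investigator is the only rater.

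**There is no contradiction.** Protocol and SAP agree on the rule, the ITT definition foresees premature discontinuation, and loss from PP is that definition working as written. This also stands: the point concerns a design choice, not an inconsistency.

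**The exception may cover the main case.** An emergency is where ethical reasons for keeping a subject would most naturally be raised. Some subjects may be retained in this way, but the term is undefined, approval is required, and the default runs the other way.

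**Much is hidden.** Redaction of the assessment schedule means that a late mRS at Early Termination cannot be ruled out. This limits the ITT illustration but not the loss from PP.

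**Conclusion.** The point holds as an avoidable loss and is worth considering, with medium confidence. Applied after dosing, the default stops no study treatment, ends scheduled visits and removes the subject from PP, while ITT retains a member whose later outcomes may be missing.

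Under the stated assumptions, one lost survivor moves an observed-case arm percentage by 3.3 points (LT3001) or 7.1 points (placebo) in either direction. With the population denominator, the shift is nil if an mRS 3-5 survivor is lost, or a fall of 6.3 or 12.5 points if an mRS 0-2 subject is lost. Each shift is small against the exact intervals, and the effect is zero if nobody is unblinded after dosing.

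A reader might infer that all follow-up ends, that the safety conclusion is at risk, or that a treatment comparison could be reversed. The documents do not support this. Early Termination assessments, follow-up of the causative AE and three-month SAE reporting continue. The primary endpoint closes at 36 hours and is largely unaffected, and no unblinding rate is given on which a larger effect could rest.

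**What to change.** Leave the present sentence in force for unblinding before the infusion has ended, and keep the duty to contact the Medical Monitor. Protocol 8.4 needs no change.

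- **Protocol 9.3.2 and SAP 3.6, unblinding after dosing:** state that it is documented with date, time and reason, is notified to the Medical Monitor, and does not by itself end participation. Scheduled assessments continue to the last visit unless consent is withdrawn. Staff who remain blinded do the mRS, NIHSS and bleeding classification where available, and ratings by unblinded staff are flagged.
- **SAP 5.5 and 6:** state that flagged values are included in the ITT summaries and listed, and that a subject whose mRS or NIHSS was rated by unblinded staff is excluded from PP.

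Change both documents together, because Protocol 14 lets the SAP prevail where they differ.

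Cost: a few sentences, a flag in the eCRF and a protocol amendment, which needs regulatory and IEC/IRB approval if classed as substantial (Protocol 15.7.1). The visits are already planned for every subject. The downside is that a few late ratings in the ITT summaries may be unblinded, but they will be identifiable.
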